8.3.8 Guidelines for reporting product complaints

[figure not shown]
Any defect in the IMP must be reported as soon as possible by the Investigator to the monitoring team that will complete a product complaint form within required timelines.

Appropriate information (eg, samples, labels or documents like pictures or photocopies) related to product identification and to the potential deficiencies may need to be gathered. The Investigator will assess whether or not the quality issue has to be reported together with an AE or SAE.

8.3.8.1 Medical device deficiencies

Not applicable.

8.7 IMMUNOGENICITY ASSESSMENTS

Not applicable.

8.8 HEALTHCARE RESOURCE UTILIZATION

Healthcare resource utilization-myasthenia gravis will be assessed according to the SoA.

Healthcare resource utilization data, associated with medical encounters due to a participant's MG, will be collected using the eCRF. Protocol-mandated procedures, tests, and encounters are excluded.

The data collected may be used to conduct exploratory economic analyses and will include:

- Number of medical care encounters due to MG, including outpatient visits (ie, general practitioner, specialists, nurse, etc.), number of emergency visits and hospitalizations.
- Duration of emergency visits and hospitalizations due to gMG (total days or length of stay).
- Number of sick day leave/day off (number of days missed from work due to usual activities due to participant's gMG condition).

Related objectives/endpoints are:

- Evaluate the efficacy of tolebrutinib compared with placebo on healthcare utilization in people with gMG.
- Annualized number of days of healthcare resource utilization over the 26-week placebo-controlled treatment period.

See Appendix 11 ([Section 10.11.7](#)).

9 STATISTICAL CONSIDERATIONS

The data from the placebo-controlled and the OLE treatment phases will be the focus of the clinical study report of the respective phase. The following statistical methods/considerations relate to the analysis of the data from the placebo-controlled period. The data from the open-label portion are non-controlled and supportive in nature; summary statistics will be provided for each of the efficacy variables and for safety data.

The null hypothesis for the primary efficacy endpoint of the change from baseline in MG-ADL score at Week 26 is that there is no treatment difference between tolebrutinib and placebo, and the alternative is that there is a between-treatment difference. To strongly control the type I error rate for the study, a procedure will be applied at a 2-sided 5% significance level. If tolebrutinib is significant for the primary endpoint, a selective set of secondary endpoints will be tested following a pre-specified procedure. The complete list of the secondary endpoints that will be adjusted for multiplicity will be detailed in the statistical analysis plan (SAP) prior to the interim database lock. The study will be declared positive at the final analysis if the null hypothesis for the change from baseline in MG-ADL score at Week 26 for tolebrutinib versus placebo is rejected.

9.1 SAMPLE SIZE DETERMINATION

A total sample size of [REDACTED] participants (randomization ratio 1:1, ie, [REDACTED] [REDACTED]) is needed to have at least 80% power to demonstrate superiority of tolebrutinib versus placebo (0.05 2-sided significance level) based on the following assumptions on the primary endpoint (change from baseline in MG-ADL total score at Week 26):

- True mean difference of -2 between tolebrutinib and placebo.
- Common standard deviation (SD) of 4.
- 15% early discontinuation from the treatment/study.

Calculations were made using East[®] 6.5.

Randomization will be stratified by MGFA class (II, IIIa/IVa, or IIIb/IVb) and region (US, non-US).

[REDACTED]

[REDACTED]

[REDACTED]

[REDACTED]

9.3 STATISTICAL ANALYSES

The SAP will be finalized prior to the database lock for the IA and will include more technical and detailed descriptions of the statistical analyses, including methods to assess the impact of missing data, subgroup analyses, etc. This section is a summary of the planned statistical analyses of the most important endpoints including primary and secondary endpoints.

9.3.1 General considerations

The baseline value of efficacy parameters is defined as the last available value prior to the first dose of the study medication unless otherwise specified. The baseline value of safety parameters is defined as the last available value prior to the first dose of IMP. For participants randomized but not treated, the baseline value is defined as the last available value before randomization.

Unless otherwise specified, analyses will be performed by treatment group (and overall for baseline and demographic characteristics).

The observation period will be divided into 4 segments:

- The pre-treatment period is defined as the period from signed informed consent up to the first IMP administration.
- The on-treatment period (ie, TE period) for the DB period is defined as the period from the first IMP administration to the earliest of 1) last IMP administration plus 10 days, 2) first IMP in the OLE, 3) death date, or 4) last contact date.
- The on-treatment period for the OLE is defined as the first IMP administration in the OLE to the earliest of 1) last IMP administration plus 10 days, 2) death date, or 3) last contact date.
- If applicable, the post-treatment period is defined as the period from the end of the on-treatment period to the last contact date.

9.3.2 Primary endpoints

A combination of treatment policy strategy and composite variable strategy will be used to handle ICEs for the analysis of the primary endpoint of change from baseline in MG-ADL total score at Week 26 in the mITT population ([Table 5](#)).

Table 5 - Intercurrent events

Intercurrent event	Strategy	Variable of interest
Permanent study intervention discontinuation before Week 26 due to a reason other than rescue therapy or lack of efficacy	Treatment policy strategy	Observed change from baseline MG-ADL total score at Week 26
Permanent study intervention discontinuation before Week 26 for rescue therapy and/or lack of efficacy	Composite variable strategy	Worst change from baseline MG-ADL total score during the 26 weeks DB treatment period before or after the intercurrent event

DB: double-blind; MG-ADL: Myasthenia Gravis-Activities of Daily Living.

Population level summary: Difference in mean change from baseline MG-ADL total score between tolebrutinib and placebo will be analyzed using an ANCOVA with change from baseline MG-ADL total score at Week 26 as the response variable, accounting for ICEs as detailed above; and treatment, baseline MG-ADL total score, and all randomization stratification factors as covariates. For participants who prematurely discontinue study intervention due to a reason other than rescue therapy or lack of efficacy and then further withdraw from the study before Week 26, their MG-ADL total score will be missing at Week 26 and therefore will not be included in the ANCOVA model. Difference in least squares means, the corresponding 95% CI and p-value will be provided for the comparison of tolebrutinib versus placebo.

Participants who prematurely discontinue study intervention, including those receiving rescue treatment, will be encouraged to continue study FU and have efficacy assessments performed at scheduled visits. These data will be included for supplementary analyses for the primary endpoint to assess the efficacy of tolebrutinib compared to placebo in an intention-to-treat (ITT) setting, ie, the assessment of the treatment policy or strategy. A mixed-effect model with repeated measures (MMRM) approach will be used with change from baseline in MG-ADL total scores at scheduled visits up through Week 26 as the response variable; and treatment, baseline MG-ADL total score, all randomization stratification factors, visit, treatment-by-visit interaction, and baseline MG-ADL total score-by-visit interaction as covariates. For participants who withdraw from the study before Week 26, MG-ADL total scores will be missing after the study discontinuation. No imputation will be performed for missing values in this supplementary analysis. An unstructured correlation matrix will be used to model the within-participant errors. Parameters will be estimated using the restricted maximum likelihood method. Statistical inference on the treatment comparison for the change from baseline in MG-ADL score at Week 26 will be derived from the mixed-effect model. Difference in least squares means, the corresponding 95% CI, and p-value will be provided for the comparison of tolebrutinib versus placebo.

Sensitivity analysis to assess the impact of missing data will be explored. Details will be included in the SAP. Additionally, subgroup analyses will be conducted to assess consistency of treatment effect. The subgroup factors will include at a minimum all stratification factors, age, gender, race and SoC. The detailed list of subgroups and additional details of the subgroup analyses will be provided in the SAP.

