6.8.3 Rescue therapy

The use of rescue therapy for gMG worsening will be allowed at any time during both the DB and OLE parts of the study at discretion of the Investigator in case of at least a 2-point increase of individual non-ocular MG-ADL items compared to the Day 1 MG-ADL value or new or worsening of respiratory/ bulbar symptoms. Rescue therapy can include IVIg, plasma exchange, change in the SoC OCS dose or any use of new CS. If rescue therapy is required, the Sponsor should be informed, preferably prior to administration of treatment, where possible, without compromising the participant's safety. The date and time of rescue therapy administration as well as the name and dosage regimen must be recorded. In case of use of rescue therapy during the DB period, the study intervention should be permanently discontinued (see [Section 7.1](#) for handling of participants after permanent intervention discontinuation).

The supply of rescue therapy will be specified at the country level.

Use of rescue therapy must be recorded in the eCRF.

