7.1 DISCONTINUATION OF STUDY INTERVENTION

7.1.1 Permanent discontinuation

Permanent intervention discontinuation is any treatment discontinuation associated with the definitive decision from the Investigator or the participant not to re-expose the participant to the study intervention at any time.

In rare instances, it may be necessary for a participant to permanently discontinue study intervention.

During the DB period, the use of rescue therapy will lead to permanent discontinuation of the study intervention.

The following may also be justifiable reasons for the Investigator or Sponsor to discontinue a participant from the study intervention:

- Adverse events that endanger the safety of the participant, or if discontinuation of study intervention is desired or considered necessary by the Investigator and/or participant.
- If IMP discontinuation criteria are met as per guidance for the FU of laboratory abnormalities in Appendix 6 ([Section 10.6](#)).
- At participant's request, ie, withdrawal of the consent for treatment.
- If a female participant becomes pregnant or wishes to become pregnant during the study.
- Any serious opportunistic infections.
- Continued need for/chronic use of a prohibited concomitant medication (see [Section 6.8](#), Appendix 10 [[Section 10.10](#)]).

Any abnormal laboratory value or ECG parameter will be immediately rechecked for confirmation after 24 hours before making a decision of permanent discontinuation of the IMP for the concerned participant.

Handling of participants after permanent intervention discontinuation

[figure not shown]
Participants will be followed up according to the study procedures specified in this protocol up to the scheduled date of study completion, or up to recovery or stabilization of any AE to be followed up as specified in this protocol, whichever comes last.

During the DB period, if possible, and after the definitive discontinuation of study intervention, the participants should be encouraged to come back as soon as possible for the pEOT visit and will be assessed using the procedures planned for the visit. Participants will be asked to continue in the study, attending all scheduled visits as per SoA ([Section 1.3](#)) if possible until the end of the DB period. If the participant does not agree to the full visit schedule per SoA after a decision for permanent end of treatment (EOT), the FU visit (4 to 8 weeks after pEOT) will be performed.

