7.1.4 Temporary discontinuation

Temporary intervention discontinuation may be considered by the Investigator because of suspected AEs or disruption of the clinical study due to a regional or national emergency declared by a governmental agency ([\[Section 10.9\]](#) Appendix 9: Contingency measures for a regional or national emergency that is declared by a governmental agency). For all temporary intervention discontinuations, duration should be recorded by the Investigator in the appropriate pages of the eCRF.

If surgery is needed during the study, the benefit-risk of withholding the IMP for at least 3 to 7 days pre- and post-surgery and the risk of bleeding should be considered.

The following shall lead to temporary treatment discontinuation:

- Cytopenias: the Sponsor's algorithms for neutropenia and thrombocytopenia as per Appendix 6 ([Section 10.6](#)) should be followed.
- Serum creatinine, creatine phosphokinase (CPK) and liver enzyme increase: follow corresponding algorithms as per Appendix 6. ([Section 10.6](#)).
- Cardiac arrhythmia (atrial fibrillation): Any Grade 3 event (symptomatic, urgent intervention indicated, device [eg, pacemaker], ablation, new onset).
- Suicidal risk as per C-SSRS: if a participant scores “yes” on items 4 or 5 of the Suicidal Ideation Section, or “yes” on any item of the Suicidal Behavior Section.

If needed, temporary treatment discontinuation can be considered by the Investigator or by the participant for any other reason, including due to any safety concerns because of disruption of the study due to a regional or national emergency declared by a governmental agency such as COVID-19 (Appendix 9 [[Section 10.9](#)]), or another illness or if there is a need for a prohibited concomitant medication. Treatment can be resumed later when it is considered safe and appropriate.

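### Table 5 scores rescue as failure only when it is the reason IMP was stopped; rescue after a stop for another reason is scored on the observed Week 26 value

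*Combined protocol and SAP*

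**What the plan says.** Table 5 (section 9.3.2) defines two intercurrent events. Both are permanent discontinuations of IMP, and they differ only in the reason for stopping.

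- Row 1: "Permanent study intervention discontinuation before Week 26 due to a reason other than rescue therapy or lack of efficacy". Treatment policy; the observed Week 26 change is analysed.
- Row 2: "Permanent study intervention discontinuation before Week 26 for rescue therapy and/or lack of efficacy". Composite; the worst change in the double-blind period is analysed, whether it came before or after the event.

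For a row 1 participant who then withdraws from the study, "their MG-ADL total score will be missing at Week 26 and therefore will not be included in the ANCOVA model". Section 9.3.3 uses the same reason-based wording for the secondary change scores and for both responder endpoints.

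Three other provisions matter.

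- Section 6.8.3: "The use of rescue therapy for gMG worsening will be allowed at any time during both the DB and OLE parts of the study". It is not limited to participants still taking IMP.
- Section 7.1.1: "During the DB period, the use of rescue therapy will lead to permanent discontinuation of the study intervention".
- Section 7.1.1, after a permanent stop: "Participants will be asked to continue in the study, attending all scheduled visits as per SoA".

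The supplementary MMRM in section 9.3.2 is treatment policy throughout and uses post-rescue scores as observed.

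**The concern.** Use of rescue is not an intercurrent event in its own right. It enters Table 5 only as a reason for stopping IMP. Once IMP has been stopped permanently for another reason, later rescue cannot be the reason for the stop, so the participant stays in row 1. The Week 26 score may then reflect IVIg, plasma exchange or extra corticosteroid, and the participant may meet the responder threshold because of it.

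The same rescue given on IMP would be scored as the worst change and as non-response. Row 2 takes the worst value even after the event, so it is built to give rescue no credit; row 1 gives that credit in full. In the visible text no analysis, primary or supplementary, counts all rescue before Week 26 as failure. If such cases were unequal between arms, the arm with more of them would look slightly better than under a rescue-keyed rule.

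**Working it through.** **1. Which rule applies**

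| Course before Week 26 | Table 5 | Primary analysis | MG-ADL responder |
|---|---|---|---|
| Rescued on IMP, or during a temporary hold (7.1.1 then makes the stop permanent because of rescue) | Row 2 | Worst change | No |
| Permanent stop for another reason, rescued later, Week 26 score obtained | Row 1 | Observed change | Yes, if the reduction is at least 2 points |
| Permanent stop for another reason, rescued later, withdraws | Row 1, score missing | Left out of the ANCOVA | No Week 26 score to meet the threshold |

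The second line is open because 6.8.3 allows rescue throughout the double-blind period and 7.1.1 keeps stopped participants in scheduled visits. No visible text reassigns these cases.

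**2. Evaluable sample size**

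N is redacted, so there is no stated figure to reproduce. Section 9.1 gives a difference of 2, SD 4, two-sided alpha 0.05, at least 80% power and 15% early discontinuation.

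- n per arm = 2 × (1.960 + 0.842)² × 4² / 2² = 62.8, so 63 evaluable (64 by the t-test).
- Randomized per arm = 63 / 0.85 = 74.1, so 75.
- Standard error of the difference = 4 × √(2/63) = 0.71.

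**3. Illustrative participant (assumed values)**

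Baseline MG-ADL 9; IMP stopped at Week 8 for another reason; score 11 at Week 12; IVIg; score 7 at Week 26.

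- Scored as in row 2: 11 − 9 = +2, non-responder.
- Scored as in row 1: 7 − 9 = −2, responder.
- Swing: 4 points.

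The +2 mirrors the rescue criterion in 6.8.3, which concerns individual items and so is only a guide to the total. The −2 is the responder threshold in 9.3.3.

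**4. Effect on the treatment difference**

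Shift per net case = swing / evaluable n per arm.

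| Evaluable per arm (assumed) | Shift per net case | Responder rate per case |
|---|---|---|
| 50 | 4/50 = 0.080 | 2.0 percentage points |
| 63 | 4/63 = 0.063 | 1.6 percentage points |
| 100 | 4/100 = 0.040 | 1.0 percentage point |

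- At 63 per arm, one net case is 0.063/2 = 3% of the assumed effect and 0.063/0.71 = 9% of the standard error.
- From two net cases on placebo to two on tolebrutinib, the shift runs from −0.13 to +0.13 in favour of tolebrutinib. It is zero if cases are balanced.
- A shift of 0.2 points (10% of the assumed effect) needs 0.2 × 63/4 = 3.15, so 4 net cases.
- The discontinuation allowance is 0.15 × 75 = about 11 per arm for all reasons, so 4 net cases would be over a third of one arm's allowance.

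An ANCOVA simulation agrees (4,000 trials, 63 per arm, SD 4, baseline covariate, one tolebrutinib value changed from +2 to −2): mean shift 0.064, 95% range 0.051 to 0.077.

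**The case against.** Row 1 is openly labelled treatment policy, and under that strategy the observed value stands whatever treatment follows. Classifying participants by the event that ended IMP is defensible: rescue long after a stop for an adverse event is weaker evidence of drug failure than rescue on drug. Section 9.3 describes itself as a summary and leaves technical detail to a SAP whose text is not in the supplied document, so the case may be settled there. The effect per case is small against the standard error, and section 7.1.1 expects few permanent stops: "In rare instances, it may be necessary for a participant to permanently discontinue study intervention".

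Most of this stands, and it makes the point minor. What remains is that Table 5 never mentions rescue after a row 1 stop, and that no visible analysis shows the result with all rescue counted as failure.

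Three stronger readings are tempting and are not supported.

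- **The rule favours tolebrutinib because of its liver risk.** The documents give no rates by arm. Section 7.1.4 lists among the triggers for a temporary hold: "Serum creatinine, creatine phosphokinase (CPK) and liver enzyme increase: follow corresponding algorithms as per Appendix 6". Rescue during a hold falls in row 2. Section 7.1.1 also allows permanent stops under Appendix 6, but that appendix is not in the supplied text, so the mix of holds and permanent stops cannot be judged.
- **The plan values rescue in three different ways.** Leaving out those who withdraw is the general missing-data rule for row 1. It applies with or without rescue, and section 9.3.2 plans a sensitivity analysis for missing data.
- **The present wording defeats what the regulator asked for.** The amendment 03 history says only that the primary method was updated after feedback on participants using rescue. The feedback itself is not shown, and the current wording may be what was agreed.

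**Conclusion.** The point holds as a minor inconsistency between the two rows of Table 5, repeated in section 9.3.3. Rescue is failure when it, or lack of efficacy, ended IMP; otherwise the post-rescue Week 26 score counts and can make the participant a responder. The reading rests on the literal row definitions and is subject to whatever the unseen SAP adds.

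The expected size is small: about 0.06 points per net case, or 0.04 to 0.08 for 100 down to 50 evaluable per arm. This rests on the assumed 4-point swing and on a sample size inferred from the stated inputs. No direction of bias is claimed. The case for acting is that the remedy is cheap and uses data already collected, and that the choice is better settled before the arms are known.

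**What to change.** Before unblinding, take one of two routes.

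**Preferred: key the event to rescue.**
- Table 5 row 2: use of rescue therapy before Week 26, whatever the IMP status, or permanent discontinuation for lack of efficacy. Composite strategy, worst change.
- Table 5 row 1: permanent discontinuation for another reason with no rescue before Week 26. Treatment policy, observed value.
- Section 9.3.3: any rescue before Week 26 counts as non-response.

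**Alternative: keep row 1 as treatment policy for later rescue.** Say so in Table 5 or the SAP, and prespecify the rescue-keyed version as a supplementary analysis of the primary and responder endpoints.

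Under either route, report by arm the number rescued after stopping IMP for another reason.

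**Cost.** Section 6.8.3 already requires the date and use of rescue to be recorded, so no new visits or data are needed. The preferred route changes the primary estimand and needs a protocol amendment; the supplementary analysis needs only SAP text. Rescue includes a changed oral corticosteroid dose or newly started corticosteroid, so under the preferred route some participants already off IMP would take their worst score for such changes. The estimate may also become slightly less favourable to the arm with more of these cases.

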9.3.3 Secondary endpoints

The secondary efficacy endpoints are listed in the objectives and endpoints table (see [Table 1](#)). Primary analyses of secondary endpoints will be based on a combination of treatment policy strategy and composite variable strategy in the mITT population.

Secondary efficacy endpoints, defined as change from baseline score at Week 26, will be analyzed in the same way as the primary endpoint, except that the respective baseline value corresponding to the endpoint will be included as the covariate in the ANCOVA model and the worst change from baseline value as stated in [Section 9.3.2](#) for participants who permanently discontinue study intervention due to rescue therapy and/or lack of efficacy will be based on the corresponding assessment.

The proportion of responders, defined as a ≥ 2 -point reduction in MG-ADL score at Week 26, will be analyzed using a Cochran-Mantel-Haenszel test, stratified by at least the randomization stratification factors, in the mITT population. Participants not reaching at least a 2-point reduction at Week 26 or permanently discontinuing study intervention due to rescue therapy and/or lack of efficacy will be considered non-responders. The relative risk comparing tolebrutinib versus placebo will be provided along with the corresponding 95% CI. The same analysis approach will be used for the proportion of responders based on QMG score; a ≥ 3 -point reduction in QMG score at Week 26.

Data collected after the premature discontinuation of study intervention will be included for supplementary analyses for the main secondary endpoints to assess the efficacy of tolebrutinib compared to placebo in an ITT setting, ie, the assessment of the treatment policy or strategy, using the same MMRM as stated for supplementary analysis of the primary endpoint in [Section 9.3.2](#), except that the respective baseline value corresponding to the endpoint will be included as the covariate. Details, including any subgroup analyses, will be included in the SAP.

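### The responder analyses do not commit to the baseline score; a continuous baseline covariate would add a few points of power if baseline is moderately prognostic

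*Combined protocol and SAP*

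**What the plan says.** Section 9.3.3 defines the first responder endpoint in these words: "The proportion of responders, defined as a ≥ 2 -point reduction in MG-ADL score at Week 26". It "will be analyzed using a Cochran-Mantel-Haenszel test, stratified by at least the randomization stratification factors", in the mITT population. For the 3-point QMG responder endpoint, "The same analysis approach will be used for the proportion of responders based on QMG score". The effect measure is also fixed: "The relative risk comparing tolebrutinib versus placebo will be provided along with the corresponding 95% CI". Participants who stop study intervention for rescue therapy or lack of efficacy count as non-responders.

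The randomisation factors are in Section 9.1: "Randomization will be stratified by MGFA class (II, IIIa/IVa, or IIIb/IVb) and region (US, non-US". Three classes by two regions make six strata.

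The continuous endpoints are handled differently. The primary ANCOVA in Section 9.3.2 has "treatment, baseline MG-ADL total score, and all randomization stratification factors as covariates". Section 9.3.3 carries that model over to the other Week 26 change scores, each with its own baseline, and the supplementary repeated-measures models also include baseline.

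Section 9.3 leaves technical detail to an SAP to be finalised before the interim database lock. Section 9 leaves to the SAP the list of secondary endpoints under multiplicity control. The documents contain no SAP text that settles the responder strata.

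**The concern.** Each responder endpoint is a cut of a change score that the plan adjusts for baseline when it is analysed as a continuous variable. A fixed reduction of 2 or 3 points is plausibly easier to reach from a high starting score, and the entry threshold of MG-ADL 6 or more (criterion I 04) invites regression to the mean. Baseline may therefore predict response.

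The responder analysis names no baseline score. The wording lets the sponsor add strata but does not require it. A CMH test also works on categories, so the continuous score cannot enter it.

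What is at stake is some power, and the removal of chance imbalance in baseline severity, on two endpoints that express clinical meaning. Validity is not at stake.

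**Working it through.** **1. The plan's own design figure.** Inputs from Section 9.1: difference -2, SD 4, two-sided alpha 0.05, power at least 80%, 15% early discontinuation, 1:1 allocation. The sample size is redacted.

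n per arm = 2 × (1.96 + 0.84)² × 4² / 2² ≈ 63 (normal approximation), or 64 with the t-test; power is 80.1% in each case. Dividing by 0.85 gives 75 to 76 per arm, or 149 to 152 in total. The inputs are coherent. I take 128 evaluable (64 per arm) as the base case and 150 as the upper case.

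**2. Implied MG-ADL responder power without adjustment.** Assume normal changes with SD 4, rounded to whole points, and a placebo mean change of -2 (not in the documents). A reduction of 2 or more is then a change below -1.5:
- placebo: Φ((-1.5 + 2)/4) = Φ(0.125) = 0.550
- tolebrutinib: Φ((-1.5 + 4)/4) = Φ(0.625) = 0.734

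With 64 per arm, the two-proportion power is 58.6%. For placebo means from 0 to -3 it is about 55% to 61%. Most of the fall from 80% comes from dichotomising the score, not from omitting a covariate.

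**3. Effect of baseline.** Simulation with 4,000 trials per row, 64 evaluable per arm, six strata and placebo mean -2. Further assumptions not in the documents: baseline about 9 (SD 2.5, floor 6), MGFA split 40/40/20, US share 30%, no missing data, no separate rescue rule. Rho is the strength of the link between a higher baseline and a larger improvement. Entries are power in %.

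| rho | CMH, randomisation strata | CMH, strata × median split | Change | Logistic, strata | Logistic, strata + baseline | Gain |
|---|---|---|---|---|---|---|
| 0 | 59.9 | 57.7 | -2.2 | 61.7 | 61.8 | +0.1 |
| 0.2 | 58.1 | 56.7 | -1.4 | 60.2 | 60.8 | +0.6 |
| 0.3 | 60.0 | 58.7 | -1.3 | 61.6 | 63.1 | +1.5 |
| 0.4 | 59.8 | 60.6 | +0.8 | 61.8 | 64.8 | +3.0 |
| 0.5 | 59.3 | 61.8 | +2.5 | 61.1 | 66.8 | +5.7 |

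The simulation standard error of one power figure is √(0.6 × 0.4 / 4000) = 0.8 points. Methods in a row share the same data sets.

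With placebo mean -1, the median split changes CMH power by -0.2 points at rho 0.3 (60.3 to 60.1) and +3.1 at 0.5 (62.1 to 65.2). Adding baseline to the logistic model gains 1.8 (62.8 to 64.6) and 5.8 (64.4 to 70.2).

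Further runs over 128 to 150 evaluable gave somewhat larger logistic gains: about 1 point at 0.2, 2 to 3 at 0.3, 4 to 6 at 0.4 and 7 to 8 at 0.5.

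**4. Separating the test from the covariate.** In every row the logistic test without baseline already exceeds CMH by about 2 points. Under no effect it rejected in 5.7% and 5.3% of trials (rho 0.3 and 0.5), against 4.9% and 4.5% for CMH. That gap is a more liberal test, not a benefit of baseline.

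**5. A comparison that holds type I error.** A baseline-adjusted risk-difference test with robust variance was compared with CMH at 128 or 150 evaluable:

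| rho | Power change against CMH (points) |
|---|---|
| 0 | -0.5 to -2.5 |
| 0.2 | about 0 |
| 0.3 | +0.5 to +1.5 |
| 0.4 | +2 to +4 |
| 0.5 | +5 to +6 |

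Its null rejection rate was 4.1% to 5.3% (simulation SE 0.4 points).

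**6. QMG.** The documents give no QMG effect or SD, so no figure is offered.

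**The case against.** The strongest reply is that the plan has not excluded baseline. The qualifier 'at least' makes the randomisation factors a minimum, and detail is left to the SAP. A reader might infer that the responder tests use the randomisation strata only and ignore baseline; the text does not support that. It shows an open choice, and this part of the reply stands.

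It also stands that stratified CMH with a relative risk is valid and light on assumptions, with simulated type I error of 4.5% to 4.9%. MGFA class already carries some severity information. The Synopsis names change in QMG and change in MGII as the main secondary endpoints, and nothing says that the responder endpoints are in the multiplicity-controlled set.

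A reader might also infer a gain of up to about 10 points. With 150 analysed, placebo mean -0.5 and rho 0.5, a logistic score test with baseline had 75.1% power against 65.5% for CMH, a gap of 9.6 points. That comparison changes the test and the covariate together, and part of the gap is the effect in step 4.

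What the reply does not remove is that using the permitted extra strata inside CMH recovers little. A median split doubles six strata to twelve, about 128/12 ≈ 11 participants each, and loses power when the correlation is weak. Using the score well needs a different method, not only a longer list of strata.

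**Conclusion.** The point holds as a low-cost improvement. The plan leaves baseline adjustment of the two responder endpoints uncommitted and names a test that cannot use the continuous score, although it adjusts the continuous endpoints from the same scales for baseline.

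For MG-ADL, adding continuous baseline to the same logistic test gains about 1 point of power at a correlation of 0.2, 2 to 3 at 0.3, 3 to 6 at 0.4 and 6 to 8 at 0.5, taking all runs together. Against the planned CMH, with type I error held, the realistic gain is about 0 to 6 points over that range. If baseline is not prognostic there is a loss of about 0.5 to 2.5 points.

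These sizes rest on an assumed sample size, baseline distribution, strata mix, placebo change and correlation, none of which the documents give. They do not carry over to QMG. The documents do not support a claim of bias, of an invalid test, or of a deliberate decision to leave baseline out.

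**What to change.** In the SAP, before the interim database lock:

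- Make the main analysis of each responder endpoint a logistic regression with treatment, the matching continuous baseline score (MG-ADL or QMG), MGFA class and region, in the mITT population with the existing non-responder rule.
- Report the relative risk, which the plan already promises, and the risk difference, both standardised over the mITT population with robust 95% CIs.
- Base the test on the robust standardised estimate rather than on the logistic likelihood or score test. State the small-sample form of the variance, and check type I error at the actual sample size.
- Keep the stratified CMH test as supportive.

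If the sponsor prefers CMH as the main test, the SAP should at least replace the open wording with the exact list of strata.

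The cost is SAP text and a few lines of code, with no new data or participants. The downside is a model-based estimate and a point or two of power lost if baseline does not predict response.
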